4.2.2 Reference Safety Information

Nabiximols is a licensed medicine containing THC and CBD as active pharmaceutical ingredients. A thorough review of the safety of the two important phytocannabinoids have been undertaken and reported in the nabiximols SPC.

5. STUDY OBJECTIVES

- The primary objective is to evaluate the effectiveness of the treatment regimen on reducing the average intensity of pain of subjects with chronic non-cancer pain compared to matched controls.
- The secondary objective is to evaluate the effectiveness of the treatment regimen on quality of life measurement, global impression of change, well-being, appetite, sleep scores and changes in concomitant medicine of chronic non cancer pain sufferers compared to matched controls.
- Safety and tolerability of the treatment regimen in chronic non-cancer pain subjects will also be assessed.

6. INVESTIGATIONAL PLAN

6.1 Overall study design and plan

This is a non-randomised, non-blinded single arm real world data collection study investigating the safety, tolerability and effectiveness of medicinal cannabis in chronic non-cancer pain subjects. The study will be conducted in a CBMP treatment clinic that has staff experienced at administering and managing the use of CBMP in its current unlicensed status. At time of enrolment, baseline data will be provided by the participant's health care team who is managing their chronic non-cancer pain (to current standard of care) and collected at the clinical study site. This will provide information on the type of chronic non-cancer pain the subject has (including relevant investigations previously conducted) and the types of drugs and non-pharmacological interventions that the subject is receiving or has received. The standard of care treatment and patient management will be determined by the treating physician. All study treatments and/or any change to treatment or management of the disease that occur throughout participation in the study will be recorded as well as being communicated to the subject's GP. Data will be collected either by the Physician during the study visit or via real time collection via an application (ePRO) provided to the subject. Data will be collected retrospectively and prospectively. A sample size of 5000 participants is planned.

[figure not shown]
Trial subjects will come from patients who have consented to receive treatment at the Harley Street (CPC) clinic. The study will consist of an initiation visit (or call) to allow screening and base line data to be taken and then a follow up visit (or call) every three months thereafter, until the end of the study (after the last subject's 3 years of treatment). Day 0 (baseline) for each subject will be the initiation visit when study treatment is started (first prescription written) (see figure 1). Prior to conducting any data collection, eligibility for enrolment will be assessed, oral consent will be requested for conductance of a genetic test and if appropriate a pregnancy test. A full medical history will be taken to assess suitability for treatment with medical cannabis; focusing on pain aetiology, subject's current standard of care and previous history of medical cannabis, if any use. Each participant will be provided with study documents to allow them to consider whether they want to have their data collected prior to providing written informed consent.

Informed consent documents (consent form and patient information sheet) will be sent to patients at least 2 days prior to the initial consultation to allow patients time to review them. At the time of initial consultation, the clinician will review the documents with the participant again and explain them in detail. If the subject agrees to provide informed consent, the clinician will witness the subject signing the consent form. If this takes place over video conference the clinician will witness and record the signing event. In addition, the subject will provide photographic identification prior to consultation, permitting confirmation of the participants identification at the time of the remote consultation. Free prescriptions for the study regimen will be provided. Subjects will provide saliva samples for genetic single nucleotide polymorphism (SNP) genetic analysis to study the genetic risk of an individual's sensitivity to THC. Subjects will be continuously monitored via real time reporting of patient reported outcomes and cannabis use information delivered by vaporiser and its bluetooth connected mobile phone application. Tolerability-related patient reported outcome

data will trigger automatic alerts to clinicians who will contact those subjects for assessment. Subjects will have quarterly consultations with specialists to discuss their treatment and to collect adverse events, until the end of the 3 years of treatment. On each 3 monthly follow up, an updated medical history will be taken, alongside information on current standard of care treatment and a review of the CBMP prescribed will be undertaken (see figure 1).

Under the supervision of an appropriately qualified and trained physician, all subjects will be prescribed a dose of CBMP product that is appropriate for their type of chronic non-cancer pain, their medical history and their previous experience with cannabis. Cannabis tolerance will be monitored via ePRO data collection with tolerability questions asked after each vapourisation session. After 1 month of treatment at the low dose, this information will be used, alongside regular monitoring of the subject, to guide the Investigator on whether the subject can be titrated to the higher dose. The length of the trial for each participant is 3 years. Treatment will continue until the end of the study (see figure 1). An overview on the study procedures is given in the schedule of assessments (Table 1-1).

Figure 1; schematic of patient journey

Stage 4	
Clinic treatment phase
 
Predominantly application-based data collection, video consultation/face-to-face reviews at 3-month timepoints. Review tolerability, treatment effects and concomitant changes to standard of care
 
Patients asked if they want to join CANPAIN study and are provided with PIS about study and draft study consent form.
 
If they want to enter study inclusion/exclusion criteria confirmed and meeting arranged to review study consent form and get it signed.
 
Study protocol followed for this patient from this point on until end of maximum of 3 years

---------	--

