	
Statistical analysis, data listings, graphs and summary tables will be produced using SAS®, version 9.2 or above.
 
Full details, including the use of the matched control database(s), of the interim and final statistical analyses to be performed will be described in detail in the Statistical Analysis Plan (SAP).

--	---

DRAFT

Table 1-1: Schedule of Assessments

	Initiation visit Day 0 (Baseline)	Daily data collection	Weekly data collection	Monthly data collection	Follow up visits (every 3 months ^a)
Pre-read of patient information sheet and informed consent document	X				
Written Informed Consent	X				
Check of inclusion/exclusion criteria	X				
Demographic data	X				
Medical history	X				X
Standard of care medication (number of doses given in previous period of time)	X		X		X
Site of pain reported in NRS	X		X		X
Additional efficacy assessments			X		
Quality of life score	X				X
Blood reports ^b	X				X
Genetic test for cannabis tolerance validation study	X				
Continuous cannabis intolerance assessments: red flags		X			X
Overall assessment of efficacy and tolerability			X		X
Scan or additional tests ^b	X				X
Determination of state of disease	X				X
Adverse events	X	X	X		X
Prescription and treatment regimen compliance	X		X		X

a. Follow-up visit can be done in person or over the phone. If available.

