6.6.1 Assessments during the study

- **Initiation visit/call (Day 0)**

Day 0 (baseline) for each subject will be the initial clinic visit when treatment is started. Alongside the daily monitoring of CBMP tolerability through the patient reported outcomes,

subjects will have 3 monthly consultations..

- Complete medical questionnaire form
- Review of medical history and relevant investigations
- Review current treatment being received or proposed
- Assess inclusion and exclusion criteria
- Written informed consent obtained
- Discuss the medicinal cannabis therapy
- Go through dosing instructions with participants (i.e., how to use the device, when to use the CBMP and how to enter data onto their smart device).
- If appropriate arrange the prescription

Daily assessments (concomitant with dosing)

- Tolerability NRS measurements (anxiety, drowsiness, dizziness, shortness of breath)

The tolerability measures collected 30 minutes after dosing with the CBMP are collected and fed back to Heydoc. Any NRS score >5 causes an alert, which triggers a study physician to contact the subject to assess their status and to elicit an appropriate response.

Weekly assessments

- Efficacy NRS measurements (pain, well-being, sleep quality, fatigue, nausea, depression, appetite)
- Global impression of change

3 monthly assessments

- Quality of life (SF-12)

3 monthly visits/call

- Review of efficacy and tolerability of medicinal cannabis and establishing the subject's overall impression on how they have responded to the CBMP
- Review current treatment being received or proposed
- Adverse events
- Renew prescriptions. Remind the participants of dosing instructions

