7.2 Assessment and reporting of adverse events

The occurrence of adverse events will be assessed by non-directive questioning of the participant at each visit. Further, adverse events volunteered by the participant during or between visits or detected through observation, physical examination, laboratory test, or other assessments during the observation period, will be documented. Participants will be instructed that they must immediately report any adverse events, subjective complaints or objective changes in their well-being to the study doctor or the clinic personnel, regardless of the perceived relationship between event and test product.

All AEs will be recorded by the study doctor or clinic personnel in the CRF and subject notes from the signing of informed consent until the end of the trial (3 years of treatment). The AEs will be followed until resolved, if applicable.

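### The draft CANPAIN protocol puts study entry at the first-prescription visit in its text and schedule, but within the clinic treatment phase in Figure 1 Stage 4

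*Protocol*

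**What the plan says.** All references are to Appendix 1, the draft CANPAIN protocol, unless stated otherwise.

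**Text and schedule.** Section 6.1 fixes the origin: "Day 0 (baseline) for each subject will be the initiation visit when study treatment is started (first prescription written". Consent papers go out at least 2 days before the initial consultation and are reviewed there with the clinician; then "If the subject agrees to provide informed consent, the clinician will witness the subject signing the consent form". Section 6.6.1 repeats the origin, "Day 0 (baseline) for each subject will be the initial clinic visit when treatment is started", and lists eligibility assessment and written consent under that visit. Table 1-1 marks written consent and the row "Check of inclusion/exclusion criteria" in the Day 0 column only.

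**Figure 1, Stage 4.** This stage is labelled as the clinic treatment phase and includes 3-monthly reviews of tolerability and treatment effect. Within it, "Patients asked if they want to join CANPAIN study and are provided with PIS about study and draft study consent form". Next, "If they want to enter study inclusion/exclusion criteria confirmed and meeting arranged to review study consent form and get it signed". Finally, "Study protocol followed for this patient from this point on until end of maximum of 3 years".

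**What depends on entry.** Section 9.3 builds the ITT set from everyone recruited, and the safety set from participants who have taken a dose. Section 7.2 records adverse events "from the signing of informed consent until the end of the trial (3 years of treatment", and section 7.3 opens the window for serious events at the same point. Section 6.2 makes every analysis a change from baseline. Section 9.5.1.1 takes the pain difference between study start and study end.

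**The concern.** Section 6.1 refers the reader to Figure 1 in the sentence that defines Day 0, and the visible part of that figure describes a different route into the study. On the text route, every enrolled patient is observed from the first prescription. On the Stage 4 route, a patient is already in the treatment phase when asked to join, so recruitment can depend on having stayed on treatment.

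The analysis sets and the adverse event record are both defined by study entry. A late entry point would remove early stoppers and early events from the planned results. Matching to controls cannot restore patients who never entered.

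**Working it through.** No arithmetic applies, so the check sets the passages side by side and follows patients through each route.

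**Step 1. The two routes.**

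| Event | Sections 6.1, 6.6.1 and Table 1-1 | Figure 1 Stage 4 |
|---|---|---|
| Study information given | Before the initial consultation | In the treatment phase |
| Eligibility check | Day 0 | After the patient expresses interest, in the treatment phase |
| Study consent signed | Initial consultation, Day 0 | Separately arranged meeting in the treatment phase |
| Study procedures begin | Day 0, first prescription | After the Stage 4 consent step |
| Day 0 or baseline | Visit when treatment starts | Not mentioned |

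The first four rows disagree. The last does not: Stage 4 is silent on Day 0, so the definition in the text stands. Even if the invitation came very early in Stage 4, a separate signing meeting in the treatment phase does not match signing at the initial consultation.

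**Step 2. Consequences if Stage 4 is followed.**

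- *A patient who starts treatment and stops before being invited* is never recruited, so is not in the ITT set. The patient is not a participant either, so is not in the safety set (section 9.3).
- *A patient who has an adverse event and enrols later* has that event before the window in sections 7.2 and 7.3 opens. This reads the consent in those sections as study consent, which fits section 10.3, where written consent precedes study entry.
- *Baseline for a late entrant.* Section 6.1 links the supply of baseline data to enrolment, and section 9.5.1.1 speaks of study start rather than Day 0. If the two dates differ, an on-treatment score could be taken as the starting value.

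**Step 3. Do other provisions repair this?**

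- Section 6.1 allows data to be collected backwards as well as forwards in time, and section 6.2 makes the care repository the trial database. These can recover earlier data for patients who later enrol, but not for those who never do.
- Section 6.4.8 follows subjects who discontinue treatment, which presupposes enrolment.
- The flowchart in section 9.1 accounts for people who do not enter, but as counts, without outcomes or adverse events.

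Baseline is therefore largely recoverable. The missing early stoppers are not.

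**Step 4. Size.** A figure would need the interval from first prescription to invitation and the stopping rate over it. The documents give neither. The direction is also open: losing early stoppers could flatter the treated group, while an on-treatment starting score could shrink the measured change.

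**The case against.** The strongest reply is that this is one cell of a partly visible figure in an appended draft. Stages 1 to 3 are not in the text at hand, and Stage 4 does not date the invitation. Two text sections and the schedule agree with each other, and under them no problem arises. The draft did not receive a favourable ethics opinion and is to be revised for resubmission (feasibility protocol, section 2). All of this stands. It makes the consequences conditional and the point modest, but it does not remove the conflict, and when consent is taken cannot be left to an analysis plan.

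Three stronger readings are tempting, and the documents do not support them.

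- *That time zero is undefined.* Sections 6.1 and 6.6.1 define Day 0 expressly, and Stage 4 does not redefine it.
- *That the 12-month outcome moves later into treatment.* Section 9.2 counts 12 months from baseline, which section 6.1 ties to first prescription. A shift appears only if baseline is redefined as entry and a delay is assumed. The three years in Stage 4 are a maximum and do not force longer follow-up.
- *That the pre-treatment pain score is lost.* The clinic pathway in section 2 of the feasibility protocol has patients complete pain and quality-of-life questionnaires before the first dose, and section 6.1 permits retrospective collection. What is missing is a statement that this score is the baseline.

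Nor does this establish an error in the feasibility study itself, which has no such analysis sets or 12-month comparison.

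**Conclusion.** The contradiction is real and limited. The draft fixes Day 0 but gives two incompatible accounts of when patients are invited, checked for eligibility and consented. If entry follows sections 6.1 and 6.6.1 and Table 1-1, nothing is lost. If it follows Stage 4, patients who stop before invitation are absent from both analysis sets, adverse events before consent are outside the recording window, and the starting pain score in section 9.5.1.1 is open to misreading. No size or direction of bias can be stated.

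The conclusion assumes that Stage 4 means what it says and that the unseen stages do not already place study consent at the first prescription. It should be corrected before resubmission. Confidence is medium because of the missing stages and the undated invitation.

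**What to change.** 1. Reconcile Figure 1 Stage 4 with sections 6.1 and 6.6.1 and Table 1-1, so that study consent and the eligibility check are completed at or before the initiation visit.
2. In section 9.5.1.1, define study start as Day 0 and name the questionnaire completed before the first dose as the source of the baseline pain score.
3. If anyone does consent after starting treatment, flag them, keep them in the ITT set as section 9.3 requires, and add a sensitivity analysis without them.

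The cost is one figure cell, one definition and one sensitivity analysis in a draft that is to be resubmitted anyway; the pre-treatment questionnaire is already part of the clinic pathway. The real downside is accrual: taking consent only at or before treatment start closes off patients already under treatment and may slow progress towards 5000.

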6.2 Discussion of study design and choice of control groups

The aim of the study is to evaluate whether the addition of medical cannabis to standard of care or at the completion of standard of care is beneficial with regards to pain scores, quality of life, quality of sleep and changes in the use of concomitant medication, as well as being safe and tolerable in subjects suffering from chronic non-cancer pain. The study will utilise a combination of patient reported outcomes and data from the NHS (chronic pain diagnosis, standard of care and health related laboratory tests) to provide a holistic evaluation of the CBMP treatment when combined with standard of care. The patient reported outcomes and NHS data will be transferred into an electronic health repository which will manage their day to day care, provide reports and alerts on the tolerability of the cannabis for each subject and will form the clinical trial database. The matched controls will exclude those potential participants who are consuming illicit cannabis, identified by drug screening. If participants are using illicit cannabis, they will be given the option to stop with a 3-week wash out period. If participants are not willing to cease, they will not be eligible for inclusion in the matched control cohort.

Controls

The analyses of effectiveness will be conducted through comparison with matched controls obtained from NHS sites established to enable data collection from consented subjects receiving standard of care only. Subjects who consent to have their data collected will be asked to provide essential demographic information, details on their chronic pain type, their standard of care and whether they are currently using medical cannabis to help with their pain. This information will be used to match the subject to subjects on the trial. The data collected in the match cohort will mirror the data collected from the CANPAIN minus tolerability data which will not be required.

The CANPAIN study will follow a pragmatic, real-world, 'all-comers' design with wide inclusion criteria, which is designed to result in a more representative sample of the target population and of the matched controls. Baseline characteristics of treated participants may still differ systematically from those of the matched control group and one must account for these systematic differences when estimating the effect of treatment on outcomes.

In order to reduce bias and to balance the distribution of covariates in the treated and control groups, multiple regression analysis will be used adjusting for potential confounders. Matching methods such as propensity scoring methods may also be used. The propensity score facilitates the construction of matched sets with similar distributions of the covariates, without requiring close or exact matches on all of the individual variables. However, unmeasured confounding may still be present after matching and should be recognized as a limitation.

Baseline Controls

All analyses will be baseline-compared (i.e. using changes from baseline).

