
Design
	
This trial will be conducted in a single private health clinic, staffed by clinicians experienced in prescribing and managing the use of medicinal cannabis or who will be trained to do so. The trial will use established treatment protocols which originate from experienced healthcare practitioners working at established medical cannabis clinics in comparable healthcare environments to the UK. Participant's data will be collected as they are treated.
 
The trial is an open-label, real-world study reporting on the treatment outcomes across a range of chronic non-cancer pain disorders.
 
This is a prospective trial to determine the effects of medical cannabis ("Treatment") in chronic non-cancer pain subjects on:
 
 • Pain NRS • Quality of Life (QoL) • Sleep quality NRS • Anxiety NRS • Fatigue NRS • Nausea NRS • Depression NRS • Shortness of breath NRS • Dizziness (NRS) • Appetite (NRS) • Global Impression of Change (since commencing treatment) • Personal Wellbeing Score (NRS) • Changes in concomitant analgesic medication use 
and to assess the safety and tolerability of adding medicinal cannabis to the subject's standard of care.

Planned number of participants
	
Planned sample size of 5000 participants.

Enrolment criteria
	
Inclusion criteria
 
 1. Male or female 18-85 years old; 2. Diagnosed with chronic non-cancer pain and; 3. A consented patient at the Harley Street (CPC) clinic 4. Is receiving standard of care therapy with inadequate response or has completed standard of care treatment, does not want standard of care treatment, or standard of care is contraindicated. An inadequate response is defined as the subject receiving standard analgesic agents and still has pain, has unpleasant side effects or wishes to reduce their intake of standard of care analgesic agents, e.g. a subject receiving opioids who wishes to dose reduce in light of the "opioid

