9.2 Determination of Sample Size

The sample size was calculated based on the objective of showing a greater proportion of patients experiencing an improvement in NRS score, from baseline to 12 months, when using CBMP in addition to the standard of care as compared to the standard of care alone. We assume that 25% of matched controls will experience an improvement in NRS score (O'Brien and Breivik, 2011). A sample size of 3600 patients using CBMP plus 3600 matched controls will provide at least 80% power to detect an increase in the proportion of patients experiencing a 28% improvement, using a two-sided z-test test for proportions with a Type I error rate of 5%. After adjusting for 10% non-evaluable rate and a 20% match failure rate, the sample size is 5000 CBMP patients plus 5000 matched controls.

Thus the null hypothesis $H_0: P=0.8$ is tested against the one-sided alternative $H_1: P>0.80$. Assuming that the expected pain reduction at 18 months for the treated subjects is $P_1=86\%$, a minimum sample size of 500 subjects for each type of chronic pain, with a total minimum number of 5000 subjects, is needed to design the study at 80% power, using a one-sided level 0.05 test for single proportion and the variance from the empirical estimate.

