9.5.1.1 Change in baseline pain NRS

The change in baseline pain NRS will be defined as the difference between chronic pain state at the beginning of the study versus the end of the study (after 3 years of treatment).

The primary analysis will be a difference analysis with comparison to appropriately selected matched controls. The endpoint will be tested using a two-sided z-test test to compare results between the prospectively enrolled treated participants and external matched controls. The impact of confounding factors will be reduced as much as possible by including values of important covariates in the model and by performing sub-analyses. Covariates included in the model will be selected based on:

- (1) Base line pain scores
- (2) Cannabis consumption experience and/or
- (3) Cause of chronic pain

A propensity score analysis may also be performed to match subjects between the treated and matched control groups. The propensity score is the probability of treatment assignment conditional on observed baseline characteristics. Propensity score matching entails forming

matched sets of treated and untreated participants who share a similar value of the propensity score (Rosenbaum PR & Rubin DB, 1983a and 1985).

Secondary measure outcome variables

Descriptive statistics will be presented for Quality of life changes, sleep NRS changes, Anxiety changes, confusion changes, dizziness changes, and changes in the use of concomitant medicines. Change from baseline to a number of analysis time points (including 12 months) will be assessed. Repeated measures analyses will be undertaken to allow for the evaluation of outcomes at any timepoint. In addition, multi-state modelling (MSM) will be undertaken to assess time-varying confounds. These will be described in detail in the SAP.

A comparison between treated subjects and matched control may be performed if similar endpoints are collected in both databases. Time to event analysis, multiple regression analysis for continuous and/or categorical outputs and/or propensity score analysis may be performed as appropriate.

To deal with missing data in subjects over the 3 year period, patterns of missingness will be evaluated including missing completely at random (MCAR), missing at random (MAR) or missing not at random (MNAR) will be assessed, this will be described in detail in the SAP.

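### CBMP is given only at one private clinic and controls come only from NHS sites, so the comparison cannot separate CBMP from the clinic package, and the power in 9.2 holds only for independent patients

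*Protocol*

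**What the plan says.** The structure is stated in Appendix 1 of the Protocol, the draft CANPAIN protocol.

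- **Treated patients.** Synopsis, Design: "This trial will be conducted in a single private health clinic". Section 6.1: "Trial subjects will come from patients who have consented to receive treatment at the Harley Street (CPC) clinic". Sections 6.1 and 6.6.1 describe what they receive there besides the product: real-time reporting through an app, clinician contact triggered by tolerability scores, and a specialist consultation every three months.
- **Controls.** Section 6.2: "The analyses of effectiveness will be conducted through comparison with matched controls obtained from NHS sites established to enable data collection from consented subjects". These subjects are on standard of care alone. Their data mirror the treated cohort's except for tolerability, which is the information that triggers the alert calls.
- **Sizing.** Section 9.2: "A sample size of 3600 patients using CBMP plus 3600 matched controls will provide at least 80% power", "using a two-sided z-test test for proportions with a Type I error rate of 5" per cent. The control rate is given as "We assume that 25% of matched controls will experience an improvement in NRS score".
- **Primary test.** Section 9.5.1.1: "The endpoint will be tested using a two-sided z-test test to compare results between the prospectively enrolled treated participants and external matched controls". The covariates named there are baseline pain, cannabis experience and cause of pain. Section 9.1 matches 1:1 on demographic, socio-economic, pain and health variables.
- **Claim and caveat.** The primary objective in section 5 is the effectiveness of the treatment regimen against matched controls. Section 6.2 accepts that baseline characteristics may differ systematically and that unmeasured confounding may remain after matching. It does not mention clinic or site.

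**The concern.** There are two separate problems.

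The first concerns what is being estimated. No patient receives CBMP through an NHS control site, and no control is recruited at the private clinic. An indicator for the clinic would be identical to the treatment indicator, so no model fitted to these data can tell them apart. Closer monitoring, more specialist contact or anything else peculiar to the clinic would appear in the result as an effect of CBMP. Matching on patient characteristics does not touch this, because clinic is not a patient characteristic and there is no overlap to match within.

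The second concerns precision. Outcomes of patients at the same NHS site may be correlated. The power in 9.2 comes from a test of two proportions with no allowance for that, and the condition is not stated. If the correlation is not negligible, the planned intervals are too narrow and the stated power is too high.

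**Working it through.** **Inputs from the documents.** Evaluable patients n = 3600 per group, two-sided 5%, control rate 25% (all 9.2). The 28% in 9.2 is ambiguously worded and is read here as the treated proportion. That reading needs 3397 per group for 80% power. A 28% relative increase (25% v 32%) would need 652, and a 28-point increase (25% v 53%) would need 47. Only 25% v 28% is near 3600.

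**Reproducing the plan's figures, patients independent.**
SE = √[(0.28×0.72 + 0.25×0.75)/3600] = 0.0104, or 1.04 points.
Power = Φ(0.03/0.0104 − 1.96) = 82%, which meets the stated floor of 80%.
Inflation: 3600/(0.9×0.8) = 5000. Both figures stand under independence.

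**Problem 1: a fixed clinic difference and no CBMP effect.**
With the variance at 25% in both groups, SE = √(2×0.25×0.75/3600) = 0.0102.
- Clinic difference of 1 point: 0.01/0.0102 = 0.98, and the test rejects about 16% of the time.
- Clinic difference of 3 points: 0.03/0.0102 = 2.94, Φ(2.94 − 1.96) = 84%. With the treated variance taken at 28% this equals the 82% power above, as it must, because a 3-point clinic difference looks the same to the test as the 3-point CBMP effect it was sized for.

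More patients shrink the SE but leave the clinic difference unchanged.

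**Problem 2: clustering of the controls only.** The ICC and number of sites K are assumptions, with equal-sized sites.
Control design effect: DE = 1 + (3600/K − 1)×ICC.
Type I error of the plain z-test: 2Φ(−1.96×√[2/(1 + DE)]).
Power with the correct SE: Φ(0.03/√[(0.28×0.72 + 0.25×0.75×DE)/3600] − 1.96).

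| K | ICC | DE | Type I error | Power |
|---|---|---|---|---|
| 20 | 0.001 | 1.18 | 6.0% | 79% |
| 20 | 0.005 | 1.90 | 10.3% | 67% |
| 20 | 0.01 | 2.79 | 15.5% | 56% |
| 20 | 0.02 | 4.58 | 24.1% | 42% |
| 50 | 0.001 | 1.07 | 5.4% | 81% |
| 5 | 0.001 | 1.72 | 9.3% | 70% |

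Worked example, K = 20 and ICC 0.005: DE = 1 + 179×0.005 = 1.90; 1.96×√(2/2.90) = 1.63; type I error 10.3%.

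For scale, the between-site SD of the responder rate is √(ICC×0.25×0.75). At ICC 0.005 that is 3.1 points, about the difference the trial is sized to find.

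**The case against.** Several counter-arguments have force.

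- **Variance details belong in the SAP.** Only 9.2 speaks of proportions. Section 9.5.1.1 allows covariates and states no variance formula, and a z-test from a model with site-robust errors would satisfy it. This stands: the protocol does not forbid clustering. What remains is that 9.2 states its power without the condition it depends on. No SAP can recover the CBMP-versus-clinic contrast.
- **P-values are descriptive.** Section 9.1 calls the analyses exploratory and disclaims type I error control. So 5% is a design parameter rather than a protected error rate. It is still the basis for 5000 patients per group, and 95% intervals will be reported.
- **Confounding is already conceded.** Section 6.2 concedes it in general terms. It does not say that treatment and provider coincide completely.
- **Background care is not confined to the clinic.** The synopsis has treated patients continue standard of care with their regular practitioner, and the app and alerts are partly bound to dosing. This stands, and it is why the effect is best described as that of a clinic package. It does not restore any contrast within a site.
- **This is a draft appended to a feasibility study.** The feasibility objectives make no such comparison, and its section 2 says the next application will address concerns about the control group. This lowers the urgency.

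A reader might also infer that the true type I error is far higher. Treating the clinic as a random draw from the NHS sites, with 20 sites and ICC 0.005, 0.01 and 0.02, gives 54%, 66% and 75%. The documents do not support that reading, because nothing in them shows that a private clinic varies as NHS sites do. A fixed difference between the settings is bias, not sampling error.

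**Conclusion.** The concern holds in two parts of different strength.

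The inability to separate CBMP from the clinic package is structural and needs no assumed figure. It follows from sections 6.1 and 6.2, and the attribution in section 5 goes beyond it. Its size in points is unknown; the 84% describes what a 3-point clinic difference would do and does not estimate that difference.

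The loss of nominal error and power is conditional. With 20 NHS sites and ICC 0.001 to 0.02, control clustering gives a type I error of about 6% to 24% and power of about 79% to 42%. With 50 sites and ICC 0.001 the plan's figures are nearly intact. It would therefore be wrong to conclude that 5% and 80% certainly fail, or that site-robust errors would make the comparison a test of CBMP. This should be corrected before the CANPAIN protocol is resubmitted. It is not a reason to hold up the feasibility study.

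**What to change.** 1. In sections 5, 6.2 and 9.5.1.1, name clinic as a confounder that this design cannot remove, and word the conclusion as the CBMP clinic package versus care at these NHS sites.
2. In 9.5.1.1, record NHS site for each control and use site-robust or random-effect standard errors for the controls.
3. In 9.2, state that the power assumes independent patients, and show it over a range of ICCs and numbers of sites.

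Optionally, report a second interval that adds the between-site variance estimated from the NHS sites to the single clinic's estimate. Label it a sensitivity bound, since it assumes the private clinic varies as NHS sites do. A claim about CBMP itself would need a different design, with both treatments within the same sites or several CBMP clinics.

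Items 1 to 3 cost protocol and SAP wording and one site identifier in the control data, with no extra patients. The price is a wider interval, a less favourable stated power and a narrower conclusion.
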